### **8.3.1.16 Extra-articular assessments**

The evolution of associated nonmusculoskeletal features including inflammatory bowel disease, psoriasis, uveitis (including their severity), and flare rate history will be assessed.

## **8.4 Analysis of other efficacy variables during SFE**

In order to assess long-term efficacy of CZP for subjects with nr-axSPA, the following summaries will be presented on the SFE-FAS:

- The number and percentage of subjects achieving response for all categorical variables collected at Week 156/SFE-WD (ASDAS-MI reduction of  $\geq 2.0$  or lowest ASDAS score possible, ASDAS-MI reduction of  $\geq 2.0$ , ASDAS-CII, ASAS40, ASAS20, ASAS partial remission, BASDAI 50 and SPARCC score  $< 2$ ). In addition, a 2-sided exact (Clopper-Pearson) 95% confidence interval for the percentage of subjects achieving response will be presented. As described in Section 4.2.3, the summary will include a composite endpoint analysis, observed case analysis at Week 156 and observed case analysis at Week 156/SFE-WD.
- Subgroup analysis of ASDAS-MI responders (reduction of  $\geq 2.0$  or lowest score possible) and ASAS40 responders by Age group, Gender, Symptom Duration, HLA-B27 Genotype and MRI/CRP classification (as defined in section 4.8) using the composite endpoint analysis described in Section 4.2.3 including 2-sided exact (Clopper-Pearson) 95% confidence intervals for the percentage of subjects achieving response.
- The number and percentage of subjects with ASDAS-ID, ASDAS-MD\*, ASDAS-HD, ASDAS-vHD at Week 156 (completers only) and at Week 156/SFE-WD  
\* ASDAS-MD is equivalent to ASDAS-LD. Whereas protocol amendment 5 uses ASDAS-LD throughout the SAP and Shells will continue to use ASDAS-MD in order to maintain consistency with the double-blind TFLs previously produced for this study.
- Summary statistics along with the changes from baseline for ASDAS, BASDAI (total score, individual Questions 1, 2, 3, 4 and morning stiffness [the average of Q5 and Q6 of the BASDAI]), BASFI, SI Joint SPARCC, PGADA, nocturnal spinal pain, total spinal pain, CRP and ASQoL, collected at Week 156/SFE-WD. As described in Section 4.2.3, observed data for completers only (at Week 156) in addition to observed data for all subjects (completers and subjects with early withdrawal visits) will be presented.

## **9 PHARMACOKINETICS, PHARMACODYNAMICS, AND PHARMACOGENOMICS**

### **9.1 Pharmacokinetics**

Certolizumab pegol plasma concentration data will be summarized by treatment group overall, and by Anti-CZP antibody (ADAb) status of individual subjects (as defined below), for each scheduled visit at which samples were taken, for the SS. Samples collected out of window may

be excluded from the analysis. All CZP concentrations will be reviewed after unblinding by study statistician and clinical pharmacologist to ensure all values are plausible, and values deemed anomalous will be excluded from summary statistics. For concentration data collected in the open-label period, subjects randomized to placebo will only have their OL-CZP data on or after Week 12 open-label visit presented, to ensure the subject is at steady state. For subjects randomized to CZP, their double-blind and OL-CZP data will be presented at all available visits. Geometric mean, geometric coefficient of variation (CV), 95% CIs, arithmetic mean, arithmetic SD, median, minimum, and maximum, will be presented. Geometric mean CZP plasma concentration time curves will be plotted by treatment group, and by antibody status for subjects receiving CZP.

The value of blood sample measurements that are deemed to be below the level of quantification (BLQ), will be set to half the lower level of quantification (LLOQ) for analysis purposes. The summary statistics will only be displayed if at least two-thirds of the values are above the LLOQ.

Individual subject plasma concentrations for CZP, anti-CZP antibody (ADAb) titres, ASDAS scores and dose levels versus time will be produced on the same graph. Two Y-axes on the left will represent the CZP concentrations and anti-CZP levels. The Y-axis on the right will show the ASDAS score. The x-axis will represent time (weeks) with lines showing the treatment and dose.

## 9.2 Pharmacodynamics

Not applicable.

## 9.3 Pharmacogenomics, biomarkers and cytokines

Pharmacogenomics, biomarkers and cytokine data analysis will be described in a separate analysis plan and report.

## 10.2 Subject classification

Subjects will receive an overall classification, inclusive of Baseline and Post-Baseline results, and be classified as follows based on the ADAb assay results:

- ADAb negative: no confirmed positive ADAb samples at any of the sampling time points
- ADAb positive: confirmed positive ADAb samples at one or more sampling time points
- Missing: relevant samples are missing

Subjects baseline classification will be based on the ADAb assay test results at baseline

- Pre-ADAb negative: negative ADAb baseline sample
- Pre-ADAb positive: confirmed positive ADAb baseline sample
- Missing: no baseline ADAb sample

Baseline is defined as the sample immediately prior to or on the same day as first treatment with CZP. For subjects randomized to CZP, baseline will be Week 0 of the randomized treatment period and for subjects who were randomized to placebo but then received OL-CZP, baseline will be Week 0 of escape OL-CZP.

Subjects will receive a treatment-emergent classification based on the combination of the post-baseline ADAb assay results as well as the baseline ADAb sample result

- Treatment emergent ADAb negative: (i) subjects with no confirmed positive ADAb samples at any of the sampling time points, (ii) pre-ADAb positive subjects with all post baseline samples either ADAb negative or confirmed positive ADAb but with a titre below a pre-defined fold increase from the Baseline value (the fold increase from Baseline required to meet these criteria will be defined with the development of the assay and will be included in the TFLs)
- Treatment emergent ADAb positive: (i) pre-ADAb negative subjects with one or more confirmed positive samples post baseline, (ii) pre-ADAb positive subjects with one or more confirmed positive ADAb sample post baseline with a titre above a pre-defined fold increase from the Baseline value (the fold increase from Baseline required to meet these

criteria will be the same as that defined for treatment emergent ADAb negative and will be included in the TFLs)

- Missing: relevant samples are missing

In addition to the ADAb classifications, subjects will also receive an overall nADA classification, inclusive of baseline and post-baseline results, on the nADA assay results

- nADA negative: no nADA positive samples at baseline or post-baseline
- nADA positive: one or more positive samples at baseline or post-baseline
- Missing: relevant nADA samples are missing, e.g. if subject had samples selected for nADA testing based on their ADAb levels, but there was insufficient sample left for nADA testing.
- Not Applicable (NA): If a subject was ADAb negative (i.e. had no positive ADAb samples)

### 10.3 Analysis

Immunogenicity will be assessed through summary tables and figures, and listing of individual results by subject.

All analyses will be run on the safety population, unless specified otherwise. ADAb and nADA data will be reviewed after unblinding to ensure all values are plausible, and values deemed anomalous will be excluded from summary statistics.

The number and percentage of each subject in the above classifications (ADAb and nADA) will be reported. The prevalence of immunogenicity will be reported per time point, defined as (cumulative) proportion of subjects having confirmed positive ADAb samples at any point up to and including that time point. Missing samples will not be included in the denominator.

Time to achieving treatment-emergent ADAb positivity will be analyzed based on Kaplan-Meier approach, subjects will be considered to have an event at time where treatment emergent ADAb positive is first achieved. Subjects classified as treatment-emergent ADAb negative will be censored at time of last available ADAb result. Discontinued subjects prior to Week 52 will be censored at the last ADAb result prior to discontinuation if they have not become ADAb Positive. Subjects will be summarized based on completing 52 weeks of treatment, discontinuing prior to Week 52, PBO->OL CZP and CZP->OL CZP treatment groups.

Immunogenicity data will be correlated with PK and efficacy endpoints. No formal inferential statistics (p-values) will be derived. The following types of outputs will be produced:

- Summary of ASDAS-MI responders at Week 12 and 52 as a function of ADAb titer. This will be repeated for ASAS40 responders at Week 12 and 52. This will also be presented graphically.
- Spaghetti plots of ADAb titre (Y-axis) against time (X-axis) for treatment emergent ADAb positive subjects and treatment emergent ADAb negative subjects separately for CZP and Placebo (i.e. 4 plots). The CZP plots will have different line patterns for W52 completers and W52 discontinuers.

- Box plots of all (valid) CZP concentrations (Y-axis) versus ADA b titer (X-axis), Y-axis presented in linear and logarithmic scale.

Immunogenicity will also be correlated with possible safety findings.

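### SAP 10.3 splits the Kaplan-Meier curves for time to treatment-emergent ADAb positivity by later completion, discontinuation or switch, and names no pooled curve for subjects starting CZP

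*SAP*

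**What the plan says.** SAP Section 10.3 plans a Kaplan-Meier analysis in which the event is the first time a subject becomes treatment-emergent ADAb positive. The grouping is given in one sentence: "Subjects will be summarized based on completing 52 weeks of treatment, discontinuing prior to Week 52", which then adds PBO->OL CZP and CZP->OL CZP as the remaining groups. No group of all subjects randomized to CZP, or of all subjects starting CZP, is listed.

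The censoring rule for leavers begins "Discontinued subjects prior to Week 52 will be censored at the last" and continues that the last ADAb result before discontinuation is used, for those not already positive. Treatment-emergent negative subjects are censored at their last available result.

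The same section plans two other summaries that are not split by completion. "All analyses will be run on the safety population, unless specified otherwise", so both use the Safety Set:

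- "The number and percentage of each subject in the above classifications" is reported. Section 10.2 makes treatment-emergent status one of these classifications: "Subjects will receive a treatment-emergent classification based on the combination of the post-baseline" and baseline sample results.
- "The prevalence of immunogenicity will be reported per time point, defined as (cumulative) proportion of subjects having confirmed positive" samples up to and including that time point, with missing samples left out of the denominator.

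For subjects randomized to placebo who move to open-label CZP, Section 10.2 takes Week 0 of the open-label escape as the immunogenicity baseline.

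**The concern.** A Kaplan-Meier curve describes a group that can be identified at its time origin. Whether a subject randomized to CZP will complete 52 weeks, stop early or switch to open-label CZP is not known at the first dose. Sorting subjects by that outcome and then following them from the start conditions on the future.

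It also undoes much of the purpose of the censoring rule. Censoring leavers at their last sample is useful when they share a curve with those who stay, because they then contribute time at risk until they go. Once they are moved out, the completer curve has no drop-out to handle, and the discontinuer curve contains only subjects whose follow-up ends early.

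The split matters most if antibodies influence who leaves. The SAP does not assert this, but the link is plausible from its own text. Section 8.1.3.2 says investigators may stop study treatment in non-responders. Section 10.3 examines response by ADAb titer, and Section 9.1 examines CZP concentration by ADAb status. If positivity lowers response, it also shapes membership of the groups. At stake is how the immunogenicity results are read, not any efficacy conclusion.

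**Working it through.** The SAP gives no figure for this analysis, so there is none to reproduce. The check has two parts.

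**1. Direction.** Let T be the time to positivity and D the time of discontinuation. Apart from missed samples, every completer is observed to Week 52, so the completer Kaplan-Meier estimate is a simple proportion:

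P(T ≤ 52 | D ≥ 52) = P(T ≤ 52) × P(D ≥ 52 | T ≤ 52) / P(D ≥ 52).

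This is below P(T ≤ 52) when positive subjects complete less often than average, and equal to it when positivity and completion are unrelated.

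**2. Size.** The grouping was simulated with 400,000 subjects per scenario.

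- From the SAP (Section 10.1): post-baseline samples at Weeks 1, 2, 4, 12, 24, 36 and 52.
- Assumed, because the SAP gives no values: Week 52 incidence of 10%, 30%, 60% or 90%, with a constant hazard; overall discontinuation of 15%, 40% or 60%; discontinuation hazard ratio after a detected positive result of 1, 2 or 3.
- Simplification: no extra sample at withdrawal.
- Estimator: 1 − Π(1 − d/n) over the visits, where d is the number newly positive and n the number at risk. Subjects not yet positive are censored at their last sample.

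Results at Week 52 for 30% true incidence and 40% discontinuation:

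| Hazard ratio | Pooled KM | Completers KM | Discontinuers KM | Crude proportion positive |
|---|---|---|---|---|
| 1 | 0.300 | 0.301 | 0.217 | 0.226 |
| 2 | 0.300 | 0.263 | 0.338 | 0.232 |
| 3 | 0.301 | 0.238 | 0.417 | 0.237 |

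- **Completer gap.** It is 0.300 − 0.263 = 0.037 at a hazard ratio of 2, and 0.301 − 0.238 = 0.063 at 3.
- **Range over all scenarios with hazard ratio 2 or 3.** The smallest gap is 0.899 − 0.894 = 0.005 (incidence 90%, discontinuation 15%, hazard ratio 2). The largest is 0.601 − 0.474 = 0.127 (incidence 60%, discontinuation 60%, hazard ratio 3). That is about 0.5 to 13 points.
- **Hazard ratio 1.** Completer and pooled estimates differ by at most 0.001 in every scenario.
- **Discontinuer curve.** Even at a hazard ratio of 1 it reads low, because nobody in it has a Week 52 sample. Under the constant hazard it can reach only the Week 36 value, 1 − 0.70^(36/52) = 0.219, which agrees with the simulated 0.217.
- **Crude proportion.** At a hazard ratio of 2, the crude proportions are 0.263 in completers and 0.184 in discontinuers, and 0.60 × 0.263 + 0.40 × 0.184 = 0.231, matching the simulated 0.232 to rounding. It lies below 0.30 because subjects who leave early without a positive result count as negative.
- **Pooled curve.** It is within 0.002 of the assumed incidence in every scenario. This follows from the set-up, in which discontinuation depends only on detected ADAb status.

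**The case against.** Several points on the other side are sound.

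- **Incidence is reported.** A reader might infer that the plan gives no incidence for the treated population. It does: Section 10.3 plans the number and percentage treatment-emergent positive, and a cumulative proportion positive by time point, both on the Safety Set. The gap is narrower. The percentage makes no allowance for early leaving. The cumulative proportion, as worded, counts any confirmed positive sample and not only treatment-emergent positivity.
- **Discontinuers are not all censored.** A reader might take every discontinuer to be censored before Week 52. The rule censors only those not yet positive; a discontinuer who turned positive first is an event.
- **Bias in the completer curve is conditional.** The SAP does not say that positivity raises discontinuation, and if it does not, the completer curve is unbiased.
- **The sentence does not exclude an overall curve.** Output shells that are not shown may contain one. That is possible, but the SAP as written names only four groups.
- **Part of the remedy is already there.** PBO->OL CZP is listed as its own group, and Section 10.2 resets its baseline. Section 10.3 does not itself state the time origin for the curves.
- **A pooled curve is not assumption-free.** After Week 4 the scheduled samples are 8 to 16 weeks apart. A subject may turn positive, lose response and leave before the next sample, and censoring would then be informative. This stands and limits what the pooled curve can claim.
- **The consequence is small.** The Kaplan-Meier analysis carries no test and lies outside the hierarchy in Section 8. For the related comparisons with PK and efficacy, Section 10.3 says: "No formal inferential statistics (p-values) will be derived".

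**Conclusion.** The point holds in a limited form. For subjects randomized to CZP, the Kaplan-Meier groups in Section 10.3 are defined by status known only after the time origin, and no pooled CZP curve is named. Followed as written, the plan gives crude incidence but no censoring-adjusted incidence of treatment-emergent ADAb in subjects starting CZP.

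The completer curve understates that incidence only if positivity raises discontinuation. The size, about 0.5 to 13 points at hazard ratios of 2 to 3 and none at 1, rests wholly on assumed incidence, discontinuation and hazard ratios. It shows a range and does not predict this trial's result. The documents do not support saying that the completer curve is certainly biased.

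The groups may also overlap. A CZP subject who moves to open-label CZP before Week 52 has also stopped double-blind treatment, and no rule says which group takes precedence.

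This is a minor, descriptive matter that affects interpretation of immunogenicity only.

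**What to change.** In Section 10.3:

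- Add one Kaplan-Meier curve from first CZP dose for all subjects randomized to CZP. Censor those not yet positive at their last ADAb result before discontinuation, as the section already specifies.
- Keep the PBO->OL CZP curve and state that its time runs from first OL-CZP dose, in line with the Section 10.2 baseline.
- Label any completer or discontinuer display as descriptive only.
- State which group a CZP->OL CZP subject belongs to, and whether discontinuation in the censoring rule means stopping double-blind treatment or stopping CZP.
- Note beside the pooled curve that it assumes non-informative censoring given observed ADAb status.

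The cost is a wording change and one extra descriptive figure. No new data are needed. Section 8.1.1 refers to outputs from the Week 52 interim database lock; if those have already been issued, the curve can be added as a supplementary output.

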## 11 SAFETY ANALYSES

The SS will be utilized for safety analyses.

### 11.1 Extent of exposure

There are 4 different concepts for calculating exposure during the double-blind treatment period.

1. This approach will look at the number of doses received, which is defined as dosing days.

Days with 2 injections (i.e. at Week 0, 2 and 4) are counted as 1 dosing day if either injection is given).

2. For the CZP 200mg and placebo treatment arms, duration of exposure to study medication will be calculated as:

Date of last administration of double-blind CZP 200mg or placebo study medication – date of first administration of CZP 200mg or placebo study medication + 14 days (14 days are included in this definition as this is the dosing interval for maintenance of subjects).

If a subject dies during the exposure period (first injection to last injection + 14 days), the exposure period will end with the death date.

For subjects discontinuing from the study before Week 52, the 2-week period after last double-blind injection will be utilized.

3. For the study exposure of a subject, 5 half-lives of CZP will be taken into account. Hence, a subject will be regarded as being exposed to study drug from first double-blind injection to last double-blind injection + 70 days. The days of drug holidays beyond 70 days will be subtracted.

If a subject dies during the exposure period (1st injection to last injection + 70 days), the exposure period will end with the death date.

For subjects discontinuing from the study before Week 52, the 70 day period after last injection will be utilized.

4. This approach will be the nearly identical to approach 2. However, exposure will be censored at the first occurrence of the AE to be considered for analysis (a separate calculation has to be performed for each preferred term). The different exposure duration for the respective AEs will only be displayed in the AE tables for exposure-adjusted incidences and will not be summarized in the exposure table.

Exposure to the OL-CZP treatment will also be calculated using the above 4 methods considering only dosing during the time the subject is receiving OL-CZP study medication prior to Start of SFE. Exposure during the SFE period will be calculated using methods 2, 3 and 4 assuming first dose in the SFE period starts when the subject takes their loading dose/first dose of OL-CZP in the SFE period and ends when the subject has their last administration of study medication (or if missing, the date of withdrawal from the SFE). Total CZP incl DB and OL

exposure will be calculated using all 4 methods, by summing the exposure to CZP during the double-blind and OL- CZP periods. Total CZP incl DB, OL, and SFE OL will be calculated using methods 2, 3 and 4, by summing the exposure to CZP during the double-blind, OL-CZP and SFE periods. Note that for Total CZP incl DB, OL, and SFE OL method 1 will not be calculated as the SFE period does not collect data on dose administration. Exposure to OL-OT will not be calculated.

For the first 3 approaches, tables will summarize exposure for the placebo, CZP 200mg Q2W, OL-CZP treatment groups (split by the treatment taken during the double-blind period), SFE OL-CZP, Total CZP incl DB and OL and Total CZP incl DB, OL, and SFE OL (for methods 2 and 3 only).

The following doses will be presented in a listing:

- very first dose in the study, the very last dose in the study and the difference between them
- last dose in the DB period (i.e. last DB dose or last OL dose), the last SFE dose and the difference between them.

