### 6.4 Prior and concomitant medications

Prior medications include any medications that started prior to the start date of double-blind study medication. Past medications are a subset of prior medications, and include prior medications with a stop date before the date of first double-blind study medication administration.

Concomitant medications will be assigned to treatments according to whether they were taken at least one day in common with the treatment dosing period of that treatment as described in [Table 6–1](#). Dosing periods are defined as follows:

- For double-blind period: From first administration of double-blind medication to last administration of double-blind medication +14 days or first administration of open-label CZP, open-label other treatment or SFE period treatment, whatever comes first.
- For open-label CZP period: From first administration of open-label CZP medication to last administration of open-label CZP medication +14 days or first administration of open-label other treatment or SFE period treatment, whatever comes first.
- For open-label other treatment period: From first administration of open-label other treatment medication to last administration of open-label other treatment medication.
- For SFE period: From first administration of SFE period treatment to last administration of SFE period treatment + 14 days.

A medication can be defined as both prior and concomitant and can be concomitant to more than one treatment. Where a medication start or stop date is (partially) missing, the medication will be considered a concomitant medication, if there is the possibility of concomitant use according to the rules described in [Section 4.2.4](#). Hence, if a partial date implies the concomitant medication could have been taken concomitant to multiple treatments, it will be concomitant to all applicable treatments.

Table 6-1: Assignment of Concomitant Medications to treatments		
Period	Description	Treatment

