**Table 11–1: Assignment of Adverse Events to Study Periods**

Type of Subject	Assignment Rule Based on AE Start Date	Assignment
Subjects who do not enter the open-label period and do not enter SFE period	Start date is on or after first study drug administration during the double-blind period and on or before the last study drug administration in the double-blind period + 70 days.	Double-blind TEAE
Subjects who do not enter the open-label period but do enter SFE period	Start date is on or after first study drug administration during the double-blind period and on or before the last study drug administration in the double-blind period + 70 days and prior to the SFE period start	Double-blind TEAE

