**Table 11–1: Assignment of Adverse Events to Study Periods**

Type of Subject	Assignment Rule Based on AE Start Date	Assignment
Subjects who enter the open-label period	
1. Start date is on or after first study drug administration during the double-blind period and on or before the last study drug administration in the double-blind period + 70 days and before the start date and time of OL-CZP or OL-OT.
 
Note: If a subject continues in the study with OL-OT visits but without taking any relevant other medication, there will be no start date of the other treatment period and all AEs with a start date within 70 days after last administration will be assigned to the DB period.
	Double-blind TEAE
	
2. Start date is on or after the start date of OL-CZP and on or before the last study drug administration in the OL-CZP period + 70 days and
 
 
• before the start date of OL-OT (for subjects moving into OL-OT), or
 
• before the SFE period start (for subjects moving into SFE period)
 
	Open-label CZP TEAE
	
3. Start date is on or after the start date of OL-OT.
 
Note: Other treatment adverse events will not be summarized, but only presented in listings
	Open-label other treatment TEAE
Subjects who enter the pre-SFE period	Start date is after the last double-blind or OL-CZP dose + 70 days and is before the SFE period start.	Pre-SFE AE
Subjects who enter the open-label SFE period	Start date is on or after the SFE period start and on or before the SFE period end + 70 days.	SFE TEAE

If AE intensity or relationship is missing, then the given event will be imputed as severe or related, respectively.

The frequency of all AEs including TEAEs will be presented for each treatment group separately by System Organ Class, high level term, and preferred term. The data will be displayed as number of subjects experiencing the AEs, percentage of subjects, and number of AEs. Certain summaries will also include exposure-adjusted incidence rates and event rates. TEAEs will be summarized by treatment and period as described in [Section 3.6](#).

The following AE summaries will be presented:

- Overview of TEAE
- Overview of Pre-SFE AEs

- TEAE
- Serious TEAE
- Non-serious TEAE
- TEAE with fatal outcome
- TEAE leading to permanent withdrawal of study medication
- Severe TEAE (included in TEAE table by intensity)
- Drug-related TEAE (included in TEAE table by relationship)

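### Method-3 exposure keeps a 70-day tail that Table 11-1's event windows cut short, so double-blind and OL-CZP event rates (EAER) are divided by days on which no event can count

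*SAP*

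**What the plan says.** SAP Section 11.1, method 3, defines double-blind exposure so that "a subject will be regarded as being exposed to study drug from first double-blind injection to last double-blind injection + 70 days". Two reductions follow. One is for treatment gaps: "The days of drug holidays beyond 70 days will be subtracted". The other ends exposure at death. No cut at the start of another treatment period is stated. The same method is applied to OL-CZP, limited to doses given before SFE starts. Total CZP including SFE is formed "by summing the exposure to CZP during the double-blind, OL-CZP and SFE periods". For other treatment, "Exposure to OL-OT will not be calculated".

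Table 11-1 in Section 11.2 sets the event windows. For subjects who go into SFE, a double-blind TEAE must start within 70 days of the last double-blind dose "and prior to the SFE period start". For those who enter the open-label period, it must also start "before the start date and time of OL-CZP or OL-OT". OL-CZP events are likewise cut at OL-OT or SFE start.

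Section 11.2 uses methods 3 and 4 for the exposure-adjusted rates and gives the EAER all events over the whole exposure. Method 4 is censored at the first event, so the EAER takes method 3.

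Section 6.4 defines dosing periods for concomitant medication and does write a cut. The double-blind dosing period runs to the last dose plus 14 days or "first administration of open-label CZP, open-label other treatment or SFE period treatment, whatever comes first".

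**The concern.** A rate is interpretable only if numerator and denominator cover the same person-time. Here the denominator keeps the full 70-day tail, while the numerator stops when the next period begins. A subject who moves on within 70 days adds exposure to the old group, but events in those days go to another group. After a move to OL-OT they go to no summarized group at all, because OL-OT events are only listed and OL-OT exposure is not computed.

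Three things are at stake. EAERs for the double-blind and OL-CZP groups would be too low. The shortfall would differ between arms if one arm has more early switchers. When periods are added up for Total CZP, the tail of one period overlaps the start of the next, so the same days enter twice. The EAER appears in the TEAE, serious TEAE and withdrawal summaries and in several tables of adverse events of interest.

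**Working it through.** The SAP states no person-time or EAER figure to reproduce, so the check compares its own rules subject by subject.

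**Inputs.** 70-day tail and 14-day dosing interval (Section 11.1); last double-blind dose at Week 50 (Section 3.2.1.5), i.e. 50 × 7 = 350 days; SFE entry up to 3 months after Week 52, last SFE dosing visit Week 154, end of SFE Week 156 (Section 2.3.1); event windows (Table 11-1). Escape times, switch rates and gaps between periods are assumptions.

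**Formulas.** With last dose in week L and next period starting in week S:
- method-3 exposure = 7L + 70 days
- event window = the smaller of 7L + 70 and 7S days
- EAER shortfall at a constant event rate = 1 − window / exposure

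**Days without countable events.** Gap of 14 days: 70 − 14 = 56. Gap of 28 days: 70 − 28 = 42. Gap of 70 days or more: 0.

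**Per-subject results, double-blind period**

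| Last dose | Next period starts | Exposure (days) | Event window (days) | Shortfall |
|---|---|---|---|---|
| Week 50 | SFE Week 52 | 420 | 364 | 13.3% |
| Week 50 | SFE Week 54 | 420 | 378 | 10.0% |
| Week 50 | SFE Week 56 | 420 | 392 | 6.7% |
| Week 50 | SFE Week 60 or later | 420 | 420 | 0% |
| Week 22 | Open-label Week 24 | 224 | 168 | 25.0% |
| Week 10 | Open-label Week 12 | 140 | 84 | 40.0% |

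**Between arms (illustration only).** Assume equal true rates, escape at Week 24 by 10% of CZP subjects and by 30% to 60% of placebo subjects, and 0% to 100% of completers entering SFE at Week 52.
- 60% placebo escape, no SFE entry. Placebo: (0.6 × 168 + 0.4 × 420) / (0.6 × 224 + 0.4 × 420) = 268.8 / 302.4 = 0.889. CZP: (0.1 × 168 + 0.9 × 420) / (0.1 × 224 + 0.9 × 420) = 394.8 / 400.4 = 0.986. Apparent CZP/placebo ratio: 1.11.
- 30% placebo escape, all completers into SFE. Placebo: (0.3 × 168 + 0.7 × 364) / (0.3 × 224 + 0.7 × 420) = 305.2 / 361.2 = 0.845. CZP: (0.1 × 168 + 0.9 × 364) / 400.4 = 344.4 / 400.4 = 0.860. Ratio: 1.02.

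**Total CZP, double-blind plus OL-CZP.** A CZP subject with last double-blind dose at Week 22, OL-CZP from Week 24 and last OL dose at Week 50, not entering SFE: 224 + (26 × 7 + 70) = 476 days counted, against 350 + 70 = 420 elapsed. The excess is the 56 overlapping days.

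**Total CZP including SFE.** A CZP completer with SFE from Week 52 and last dose at Week 154:
- SFE exposure ending at the last administration, as Section 11.1 says: 420 + 102 × 7 = 420 + 714 = 1134 days
- SFE exposure with a 70-day tail: 420 + 714 + 70 = 1204 days
- Table 11-1 window, to SFE period end plus 70 days: 156 × 7 + 70 = 1162 days

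The total is 2.4% short of the event window on the first reading (1134 / 1162) and 3.6% above it on the second (1204 / 1162).

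**The case against.** The best defence is that the cut is implied. Section 11.1 introduces the four methods as exposure during the double-blind period. Section 3.2.1.2 ends that period, for switchers and SFE entrants, at the first open-label dose. OL-CZP exposure is limited to doses before SFE, and totals are built period by period. Section 6.4 concerns concomitant medication, so its wording is an analogy and not a contradiction. It stands that a cut may be intended and that two programmers could read the text differently. But the lead-in cannot supply the cut. Method 3 is built to outlast the period: a completer who does not enter SFE leaves the double-blind period at about Week 52 and stays exposed to Week 60. The OL-CZP restriction limits which doses count, not the tail after the last one.

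A reader might infer that every group is biased downward and that Total CZP is inflated by 4.9% (56 extra days on 154 × 7 + 70 = 1148). The SAP does not support that once SFE is included. The figure needs a 70-day SFE tail, whereas Section 11.1 can be read as ending SFE exposure at the last administration, and Table 11-1 counts SFE events to period end plus 70 days.

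Nor is listing OL-OT events without summarizing them an error. The plan states that choice, and it also deliberately leaves the table of events after a new biologic optional.

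**Conclusion.** The point holds, as a minor one. As written, method 3 and Table 11-1 cover different windows for double-blind and OL-CZP subjects whose next period starts within 70 days of the last dose. The EAERs of those groups are then too low: by 13.3% for a Week 50 completer starting SFE at Week 52, by more for early escapers, and by nothing once the gap reaches 70 days. These percentages assume a constant event rate. The bias is larger in the arm with more early switchers. The illustrative ratios of 1.02 to 1.11 rest on assumed escape and roll-over rates and a 14-day gap, none of which is in the SAP. SFE roll-over occurs in both arms, so its effect partly cancels between them.

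Overlapping days are counted twice when periods are summed, but the net direction for Total CZP including SFE cannot be settled from the text. The EAER carries no confidence interval or test, and no efficacy result changes.

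The EAIR has its own mismatch: method 4 follows method 2 with 14 days after the last dose, while events count to 70 days. That is a separate matter which the change below does not cure.

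**What to change.** In Section 11.1, state that method-3 exposure for the double-blind and OL-CZP periods ends at the earliest of last dose + 70 days, death, or start of the next period (OL-CZP, OL-OT or SFE), using the same start dates as Table 11-1 and the construction already used in Section 6.4. The Week 50 completer entering SFE at Week 52 then contributes 364 days, equal to the event window.

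Align the SFE method-3 end with the SFE TEAE window in the same edit. Cutting only the earlier periods would leave 364 + 714 = 1078 days against 1162 in Total CZP, 7.2% short. With both changes the total is 364 + (1162 − 364) = 1162 days, and each CZP day is counted once.

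The cost is a sentence or two in Section 11.1 and the matching dates in the exposure derivation. No new data are needed.
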